APPENDIX 1B CORTICOSTEROID RESCUE CRITERIA AND TREATMENT PROTOCOL (PART B)

Systemic corticosteroids will be avoided during PRN1008 monotherapy unless these rescue criteria are triggered, as described below, or if patients enter the study on low doses (≤ 0.5 mg/kg mg per day). In each rescue scenario, the recommended method of corticosteroid taper is shown in [Appendix 7](#).

Rescue Criteria #1: Flare which, in the mind of investigator, is potentially life threatening

- Commence conventional immunosuppressive therapy and discontinue PRN1008

Rescue Criteria #2: Development of severe (defined as PDAI score ≥ 45) but not life-threatening PV or clinically significant worsening of already severe PV during PRN1008 therapy:

- Commence, or increase dose to, full-dose prednis(ol)one (1.0 mg/kg) orally and increase dose of PRN1008 by an amount agreed to with the Sponsor's Medical Monitor to a maximum of 600 mg bid. At next review:
 - If not responding, commence conventional immunosuppressive therapy and discontinue PRN1008
 - If responding, maintain or taper corticosteroids as clinically appropriate while maintaining PRN1008 treatment.

Rescue Criteria #3: Patients with non-severe PV but who fail to achieve "Control of Disease Activity (CDA*)" by 4 weeks

- If partially responding, increase dose of PRN1008 if not already maximal (Table 4), review in 1-2 weeks, and then consider additional CS up to a dose of 0.5 mg/kg. If subsequently responding, maintain PRN1008 treatment and taper prednis(ol)one.
- If not responding, increase dose of PRN1008 if not already maximal (Table 4), review in 1-2 weeks, and then consider additional CS up to a dose of 1.0 mg/kg. If subsequently responding, maintain PRN1008 treatment and taper prednis(ol)one.

Table 4 Dose Escalation Rules Part B

Current Dose	Inadequate Clinical Response ¹ Dose-Escalation Rules
400 mg qd	Increase to 400 mg bid (allowed at Week 3 visit or later) ²
400 mg bid	Increase to 600 mg bid (allowed at Week 5 visit or later) ²
600 mg bid	No dose increase possible.

1. Investigator discretion: Generally, clinical response is shown by some improvement seen in first 2 weeks with CDA achieved by the Week 5 visit
2. Unless tolerability issues preclude dose-escalation

In each rescue scenario, the recommended method of corticosteroid taper is shown in [Appendix 7](#).

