- i. Photography is used to document skin disease changes; ideally in most patients. Strict masking of patient identity is required.

[figure not shown]
PART B: SCHEDULE OF ASSESSMENTS (24-weeks Treatment/ 4-weeks Follow Up)

[figure not shown]
	Screen	Day 1, Week 1 Pre-dose	Day 1 Week 1 Post-dose ^a	Day 2, Week 1 ^g	Day 15, Week 3 +/-3 days	Day 29, Week 5 +/-3 days	Day 57, Week 9 +/-7 days	Day 85, Week 13 +/-7 days	Day 113, Week 17 +/-7 days	Day 141, Week 21 +/-7 days	Day 169, Week 25 +/-7 days	Day 197, Week 29 +/-7 days	Unscheduled Visit
Informed Consent ^k	X												
Inclusion/Exclusion Criteria	X	X											
Height	X												
Weight	X	X			X	X	X	X	X	X	X	X	X
Physical exam/med.History PDAI, ABSIS	X												
Abbreviated physical exam., PDAI, ABSIS		X			X	X	X	X	X	X	X	X	X
ECG (12-lead)	X												(X) ^b
Vital Signs ^j	X	X		X	X	X	X	X	X	X	X	X	X
Urinalysis	X												
Hep B & C, HIV, T-spot TB Test, QuantiFERON®-TB Gold, QuantiFERON®- TB Gold Plus (QFT Plus)	X												
Pregnancy test ^c	X	X				X	X	X	X	X	X	X	
Skin biopsy ^d	X												
Hem, Coag, Chem	X ^e	X			X	X	X	X	X	X	X	X	X
FSH ^f	X												
BTK occupancy sample		X ^g	X ^h	X	X	X	X	X	X	X	X	X	(X) ^b
PK sample		X	X ^h	X ^a	X	X	X	X	X	X	X	X	(X) ^b
Anti-DSG antibodies		X				X	X	X	X	X	X	X	
Photography (Optional) ⁱ		X			X	X	X	X	X	X	X	X	X
ABQOL & TABQOL		X			X	X	X	X	X	X	X	X	X
SNAQ questionnaire		X			X	X	X	X	X	X	X	X	X
AEs		X		X	X	X	X	X	X	X	X	X	X
Concomitant Medications	X	X		X	X	X	X	X	X	X	X	X	X
Drug dispensed		X				X	X	X	X	X			
Drug reconciliation					X	X	X	X	X	X	X	X	

[figure not shown]
Schedule of Assessments Footnotes:

- a. Withhold PRN1008 on morning of Day 2 until PK/PD measurement has been taken as close to 12 hours (when *bid* dosing) or 24 hours (when *qd* dosing) after the prior dose as possible. Where follow-up on Day 2 is not possible, PK/PD samples may be taken on another day in the first week of treatment. On all other days, instruct patient to take PRN1008 in the morning as usual prior to clinic and take note of the time taken. Extra PK/PD sample intended for 1 to 5 days after dose adjustment or to replace missing samples—not required for other extra visits.
- b. Only if clinically indicated.
- c. For women of childbearing potential only. Serum pregnancy test done at screening, urine dip test done at other time points.
- d. Performed only if no suitable prior biopsy.
- e. TSH and CPK taken as part of chemistry panel.

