3.4.4 Prior medications vs. concomitant medications vs. post last dose medications

Prior medications are the medications stopped before the date of first study drug dosing.

Concomitant medications are the medications that are ongoing or stopped after the date of first study drug dosing and started on or prior to the last date of study drug dosing.

Post last dose medications are medications that started after the last date of study drug dosing.

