5.1.4 Medical History

Medical history events are reported for the following Body Systems: Skin, Head-Eyes-Ears-Nose-Throat, Respiratory, Cardiovascular, Gastrointestinal, Endocrine/Metabolic, Genitourinary, Neurological, Blood/Lymphatic, Musculoskeletal, Hepatic, Allergies, Psychological/Psychiatric and Other. The medical history events will be summarized by Body System, Starting dose and overall.

Medical history data will be listed in a patient data listing.

5.1.5 **Prior and Concomitant Medications**

All medications will be coded according to the WHODRUG dictionary WHO-DDE-B2-June 2015.

The following prior medications will be summarized by Level 2 Classification and Preferred Name for each starting dose and overall:

- Previous corticosteroid medications taken and stopped prior to date of first study drug dosing
- Other medications taken and stopped prior to date of first study drug dosing

The following concomitant medications will be summarized by Level 2 Classification and Preferred Name for each dose level and overall:

- Corticosteroid medications taken during treatment
- Corticosteroid medications started after date of last study drug dosing
- Other medications taken on or after date of first study drug dosing

Medications will be attributed to the dose level where the medication is taken during the dose level. The same medication may be attributed to more than one dose level. Corticosteroid medication started after the date of last study drug dosing will be summarized separately.

Separate listings will be provided for prior corticosteroid treatment, concomitant corticosteroid medications, post last dose corticosteroid medications, other prior medications and other concomitant medications.

5.2 **Protocol Deviations**

Protocol deviations will be identified and classified into major vs. non-major by the Sponsor prior to database lock.

The major protocol deviations will be tabulated by the deviation categories, starting dose and overall for patients who are in the ITT population.

A patient data listing with deviation category and deviation details for both will be provided for the major protocol deviations and the non-major protocol deviations.

5.3 **Study Drug Treatment Exposure and Compliance**

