Preferred Name 2.1	x (x.x)	x (x.x)	x (x.x)	x (x.x)
Preferred Name 2.2	x (x.x)	x (x.x)	x (x.x)	x (x.x)
Preferred Name 2.3	x (x.x)	x (x.x)	x (x.x)	x (x.x)
...etc...	x (x.x)	x (x.x)	x (x.x)	x (x.x)

Patients are classified into different dose levels according to the dose they received during the time the medication was taken.

Percentages are based on the number of patients in each dose group and overall.

Medications are coded using WHODD, version 01SEP2015.

ATC Level 2 Class is sorted in descending order in the Overall group. Within each ATC Level 2 Class, Preferred Name is sorted in descending order in the Overall group.

If a medication of the same ATC Level 2 Class and Preferred Name is reported multiple times for a patient, it is counted only once.

This table includes concomitant corticosteroid medications that are ongoing or stopped on or after the date of first dose of study drug and started prior to date of last dose of study drug.

Program: <program name (date, time)>, Path: <path>

Table B.14.1.6.3 Concomitant Corticosteroid Medications Started Post Last Dose (ITT Population)

ATC Level 2 Class Preferred Name	Number of patients (%)
	Overall (N = n)
Number of patients reported post last dose corticosteroid medications	x (x.x)
ATC Level 2 Class 1	x (x.x)
Preferred Name 1.1	x (x.x)
Preferred Name 1.2	x (x.x)
Preferred Name 1.3	x (x.x)
ATC Level 2 Class 2	x (x.x)
Preferred Name 2.1	x (x.x)
Preferred Name 2.2	x (x.x)
Preferred Name 2.3	x (x.x)
...etc...	x (x.x)

Percentages are based on the number of patients in the ITT population.

Medications are coded using WHODD, version 01SEP2015.

ATC Level 2 Class is sorted in descending order in the Overall group. Within each ATC Level 2 Class, Preferred Name is sorted in descending order in the Overall group.

If a medication of the same ATC Level 2 Class and Preferred Name is reported multiple times for a patient, it is counted only once.

This table includes corticosteroid medications started after the date of last dose of study drug.

Program: <program name (date, time)>, Path: <path>

Programming note for “Post Last Dose” column: N for Post Last dose column is the number of patients reported a Date of Last Dose.

Table B.14.1.7.1 Prior Medications other than Corticosteroid Medications (ITT Population)

ATC Level 2 Class Preferred Name	Number of patients (%)		Overall (N = n)
	Starting Dose 400 mg QD (N = n)	Starting Dose 400 mg BID (N = n)	

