				600 mg BID	R: xxx Level 2: xxx PT: xxxx	Start Date: ddMMMyyyy (Day x) Stop Date: Ongoing	Indication: xxx Treatment for an AE?: No Dose: xx mg Frequency: xxx Route: xxx	xxx

F=Female; M=Male

Medications are coded using WHODD, version 01SEP2015.

This table includes concomitant corticosteroid medications that are ongoing or stopped on or after the date of first dose of study drug and started prior to date of last dose of study drug.

If Date >= first dose date, then Study Day = (Date - Date of first dose +1). If Date < first dose date, then Study Day = (Date - Date of first dose).

Program: <program name (date, time)>, Path: <path>

Listing B.16.2.1.11 Concomitant Corticosteroid Medications Started Post Last Dose (ITT Population)

Starting Dose	Patient ID	Age/ Gender	Any Post Last Dose Corticosteroid med?	PRN Dose Level Prior to Last Dose of study drug	Reported Medication (R) ATC Level 2 Class (Level 2) Preferred Name/Term (PT)	Start Date (ddMMMyyyy) (Study Day)	Stop Date (ddMMMyyyy) (Study Day) /Ongoing	Indication: AE or MH No.: Dose: Dose unit: Frequency Route:	Rescue criteria
400 mg QD	xxxxxxx	xx/F		600 mg BID	R: xxx Level 2: xxx PT: xxxx	Start Date: ddMMMyyyy (Day x)	Stop Date: ddMMMyyyy (Day x)	Indication: xxx AE or MH No: AE #1 Dose: xx Dose unit: mg Frequency: xxx Route: xxx	Not applicable
				600 mg BID	R: xxx Level 2: xxx PT: xxxx	Start Date: ddMMMyyyy (Day x)	Stop Date: Ongoing	Indication: xxx AE or MH No: MH #3 Dose: xx Dose unit: mg Frequency: xxx Route: xxx	No

F=Female; M=Male

Medications are coded using WHODD, version 01SEP2015.

This table includes patients entered into follow up period and corticosteroid medications started after the date of last dose of study drug.

If Date >= first dose date, then Study Day = (Date - Date of first dose +1). If Date < first dose date, then Study Day = (Date - Date of first dose).

Program: <program name (date, time)>, Path: <path>

Listing B.16.2.1.11 Rescue Medications Taken During Study (ITT Population)

Starting Dose	Patient ID	Age/ Gender	Any corticosteroid medication?	PRN Dose Level at Medication Start	Reported Medication (R) ATC Level 2 Class (Level 2) Preferred Name/Term (PT)	Start Date (ddMMMyyyy) (Study Day) Stop Date (ddMMMyyyy) (Study Day) /Ongoing	Indication: AE or MH No.: Dose: Dose unit: Frequency Route:	Rescue criteria

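### Part B steroid tables and their listings omit a steroid started on the date of last dose, which SAP 3.4.4 counts as concomitant

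*SAP*

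**What the plan says.** Part B SAP 3.4.4 leaves no gap at the end of treatment. A medication is concomitant if, among other conditions, it "started on or prior to the last date of study drug dosing". On the other side, "Post last dose medications are medications that started after the last date of study drug dosing". Section 5.1.5 plans separate summaries of steroids taken during treatment and of "Corticosteroid medications started after date of last study drug dosing".

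The mock shells in section 6 use a different boundary. The footnotes of Table B.14.1.6.2 and Listing B.16.2.1.10, which also cover ongoing use, take steroids "stopped on or after the date of first dose of study drug and started prior to date of last dose of study drug". For Table B.14.1.6.3 the footnote reads "This table includes corticosteroid medications started after the date of last dose of study drug", and the post-last-dose Listing B.16.2.1.11 likewise takes "corticosteroid medications started after the date of last dose of study drug".

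Two parts of the protocol bear on whether a start can fall on that date. Appendix 4 (Part B, footnote a) says of visits after the first trough sample: "On all other days, instruct patient to take PRN1008 in the morning as usual prior to clinic". Appendix 1B, for a potentially life-threatening flare, says: "Commence conventional immunosuppressive therapy and discontinue PRN1008". The synopsis also places the final scheduled dose on the morning of Day 169, the day of the end-of-treatment assessment.

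**The concern.** One shell rule is strictly before the last-dose date and the other strictly after it, so the date itself belongs to neither. SAP 3.4.4 does assign it, to concomitant use. A programmer who follows the footnotes and one who follows 3.4.4 can therefore produce different counts from the same data. Any difference runs one way, towards fewer patients shown with steroid use. The two tables are the planned patient counts of steroid use during and after PRN1008, in a trial whose efficacy endpoints turn on steroid exposure.

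**Working it through.** No figure of the plan has to be reproduced. The check is to apply each inclusion rule to start dates around the last dose.

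Let S be the steroid start date and L the date of last dose. Take a steroid that is ongoing, or that stopped 14 days after L, so that the stop-date condition is met throughout.

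- Table B.14.1.6.2 and Listing B.16.2.1.10: S < L
- Table B.14.1.6.3 and post-last-dose Listing B.16.2.1.11: S > L
- SAP 3.4.4, concomitant: S ≤ L
- SAP 3.4.4, post last dose: S > L

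| Start date | B.14.1.6.2 | B.14.1.6.3 | SAP 3.4.4 |
|---|---|---|---|
| L − 1 | yes | no | concomitant |
| L | no | no | concomitant |
| L + 1 | no | yes | post last dose |

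The result is the same for ongoing and stopped steroids. The gap is exactly the day S = L. With S ≤ L in the first rule, each of the six cases (three start dates, ongoing or stopped) falls in exactly one table.

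The first footnote can be read another way, with the start-date condition applying only to stopped steroids. An ongoing steroid with S = L would then enter B.14.1.6.2. But an ongoing steroid with S = L + 1 would appear in both tables, and a stopped steroid with S = L would still appear in neither. That reading does not repair the split.

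**Can S = L occur?** It can in two ways.

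1. A patient takes the morning dose, attends clinic, and PRN1008 is stopped and a steroid started at that visit. If the last tablet was taken the day before, S = L + 1 and the steroid is counted as post last dose.
2. A completer takes the final dose on the morning of Day 169 and a steroid is started at that visit.

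**Size.** Both tables count a patient once per class and preferred name, so a patient drops out of the any-steroid rows only if no other on-study steroid is recorded. The documents do not give the number of such patients, k. Assume N = 25, the number per Part in Protocol 11.4. Then k = 0 gives 0 points, k = 1 gives 1/25 = 4 percentage points, and each further patient adds 4. In a dose-level column the denominator is the number treated at that level, which cannot exceed N, so one patient is at least 4 points there.

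**The case against.** The strongest reply is that the SAP body settles the matter. Section 3.4.4 has no missing day at the last dose, 5.1.5 describes the summary as steroids taken during treatment, and section 6 says the shells set the layout and may be adjusted. The tables may be programmed correctly under a footnote that misdescribes them. That is possible, but the footnotes are written as inclusion rules, and nothing says which text prevails. The contradiction stands.

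A second reply concerns who would be affected, and most of it stands. A reader might infer that the gap removes treatment failures in particular. Appendix 1B does not support that as the usual pattern:

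- Only Rescue Criteria #1 pairs first-step therapy with stopping PRN1008.
- Under #2, prednis(ol)one is started or raised first and PRN1008 stops only on later non-response, so the earlier steroid normally keeps the patient in Table B.14.1.6.2.
- Under #3 there is no instruction to stop PRN1008.
- Conventional immunosuppressive therapy need not be a steroid.
- Patients may enter on low-dose prednis(ol)one, which already places them in the count.

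A third reply is that steroid exposure is assessed elsewhere, and this also stands. The primary endpoint (5.4.1), the CDA and CR endpoints (5.4.2.1), cumulative steroid use (5.4.2.3) and the dose before each visit (5.4.2.4) do not select records by this rule. The rescue-medication listing, which also carries the number B.16.2.1.11, has no start-date limit, so a rescue steroid begun on the last-dose date still appears there.

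**Conclusion.** The inconsistency is real and confined to two tables and their two listings. As written, a steroid started on the last-dose date is in none of them, against SAP 3.4.4. The effect on the any-steroid count is 4 points per affected patient at an assumed N = 25. It requires that the start date equals the recorded last-dose date and that no other on-study steroid is recorded. The number of such patients is unknown and may be zero. No efficacy endpoint changes.

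A reader might carry over the two Part A patients who needed high-dose steroid (Protocol 1.4.2.1) and infer a loss of 2/25, or 8 points. The documents do not support this. Those two patients received steroid temporarily during PRN1008 treatment, which Table B.14.1.6.2 captures, and nothing says that it began on the day PRN1008 stopped.

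**What to change.** In the footnotes of Table B.14.1.6.2 and Listing B.16.2.1.10, let the start date fall on or before the date of last dose, to match SAP 3.4.4. Table B.14.1.6.3 and the post-last-dose listing need no change. The cost is two footnotes and one inequality in the code, with no new data.

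In the same edit, reconcile the other end of the definition: 3.4.4 requires a concomitant medication to be ongoing or to stop after the first dosing date, while the footnotes also admit a stop on that date. Give the two listings that share the number B.16.2.1.11 separate numbers.

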
Participant Selection Criteria:
	
Inclusion Criteria Part A and Part B (unless noted below):
 
 1. Male or female patients, aged 18 to 80 years old, with biopsy-proven (positive direct immunofluorescence and appearance on H&E microscopy), mild-moderate PV in Part A (PDAI 8 to 45) and mild-severe PV in Part B (PDAI 8 to 60) 2. Newly diagnosed or relapsing patients for whom an initial period of PRN1008 monotherapy or combination therapy with low-dose corticosteroids (≤ 0.5 mg/kg of prednis[ol]one or equivalent), is judged clinically acceptable, provided tapering of the corticosteroid treatment regimen is anticipated with good clinical response to PRN1008 3. BMI > 17.5 and < 40 kg/m² Part A only 4. Adequate hematologic, hepatic, and renal function (absolute neutrophil count $\geq 1.5 \times 10^9/L$, Hgb > 9 g/dL, platelet count $\geq 100 \times 10^9/L$, AST/ALT $\leq 1.5 \times$ ULN, albumin ≥ 3 g/dL, creatinine \leq ULN (Part A) and creatinine $\leq 1.5 \times$ ULN (Part B)) 5. Female patients who are of reproductive potential must agree for the duration of active treatment in the study to use an effective means of contraception (hormonal contraception methods that inhibits ovulation, intrauterine device, intrauterine hormone-releasing system, bilateral tubal ligation, vasectomized partner, condoms or sexual abstinence). Unless surgically sterile, postmenopausal females should have menopause confirmed by FSH testing 6. Able to provide written informed consent and agreeable to the schedule of assessments 
Exclusion Criteria Part A and Part B:
 
 1. Previous use of a BTK inhibitor. 
Patients enrolled in a previous version of this protocol who are still in their 12-week active treatment period with PRN1008 are eligible to continue treatment, initially with their current dose level, under this amended protocol for an additional 12 weeks, i.e.

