3.4.1 Baseline for PDAI, ABSIS, ABQOL, TABQOL and SNAQ scores

The value measured at Week 1 Day 1 pre-dose will be used as the Baseline value. If the Week 1 Day 1 Pre-dose result is missing and the screening result is available, then the screening result will be used as Baseline.

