5.4.1.1 Subset Analyses

The robustness of the primary endpoint results will be explored by calculating the number and percent of patients meeting the primary efficacy endpoint overall (i.e. across all doses) within the following patient subsets:

- 1) Age (< 50 years, ≥ 50 years)
- 2) Gender
- 3) Total anti-desmoglein (DSG) antibody (≥ 100, < 100 units) at baseline.
- 4) Pemphigus History Type: Newly diagnosed (≤ 6 months from screening) vs. relapsed (> 6 months from screening)
- 5) Pemphigus anti-DSG Profile at baseline: Pemphigus Vulgaris (PV) vs. Pemphigus foliaceus (PF) vs. negative anti-DSG profile, defined as follows:
 - PV: anti-DSG3 positive with anti-DSG1 negative or anti-DSG3 positive with anti-DSG1 positive.
 - PF: anti-DSG1 positive only
 - Negative anti-DSG profile: neither detectable.
- 6) Pemphigus Severity: PDAI < 15 (mild-moderate) vs PDAI ≥ 15 (moderate-severe) at baseline If screening PDAI is not available use Week 1 Day 1 Pre-dose.

A sensitivity analysis using the Completer and PP populations will be provided for each subset analysis.

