Total Anti-DSG [3][4]			
< 100 unit	x (x.x)	x (x.x)	x (x.x)
≥ 100 unit	x (x.x)	x (x.x)	x (x.x)
PDAI total activity score [3]			
n	x	x	x
Mean (SD)	x.xx (x.xxx)	x.xx (x.xxx)	x.xx (x.xxx)
Median	x.xx	x.xx	x.xx
Min, Max	x.x, x.x	x.x, x.x	x.x, x.x
Pemphigus Severity [3]			
PDAI < 15 (mild-moderate)	x (x.x)	x (x.x)	x (x.x)
PDAI ≥ 15 (moderate-severe)	x (x.x)	x (x.x)	x (x.x)
PDAI Skin Activity > 0 n (%) [3]	x (x.x)	x (x.x)	x (x.x)
PDAI Scalp Activity > 0 n (%) [3]	x (x.x)	x (x.x)	x (x.x)
PDAI Mucous Membrane Activity > 0 n (%) [3]	x (x.x)	x (x.x)	x (x.x)
ABSIS Oral Involvement > 0 n (%) [3]	x (x.x)	x (x.x)	x (x.x)

[1] Based on date of first pemphigus reported in Medical History and date of screening

[2] Newly diagnosed is defined as subjects who were diagnosed at most 180 days prior to date of screening, otherwise the subject is relapsed.

[3] Result at Week 1 Day 1. If Week 1 Day 1 is missing, then the Screening result is used.

[4] Total Anti-DSG is the sum of Anti-DSG 1 and Anti-DSG3, where at least one of Anti-DSG 1 or 3 is positive, i.e. $\text{Anti-DSG 1} \geq 14$ and/or $\text{Anti-DSG 3} \geq 9$.

Percentages are based on the number of patients in each starting dose and overall.

Program: <program name (date, time)>, Path: <path>

Table B.14.1.4.1 Medical History (ITT Population)

Body System Code	Number of patients (%)		
	Starting Dose 400 mg QD (N = n)	Starting Dose 400 mg BID (N = n)	Overall (N = n)
Number of patients reporting any medical history	x (x.x)	x (x.x)	x (x.x)
Skin	x (x.x)	x (x.x)	x (x.x)
Head, Eyes, Ears, Nose, Throat	x (x.x)	x (x.x)	x (x.x)
Respiratory	x (x.x)	x (x.x)	x (x.x)
Cardiovascular	x (x.x)	x (x.x)	x (x.x)
Gastrointestinal	x (x.x)	x (x.x)	x (x.x)
Endocrine/Metabolic	x (x.x)	x (x.x)	x (x.x)
Genitourinary	x (x.x)	x (x.x)	x (x.x)
Neurological	x (x.x)	x (x.x)	x (x.x)
Blood/Lymphatic	x (x.x)	x (x.x)	x (x.x)
Musculoskeletal	x (x.x)	x (x.x)	x (x.x)
Hepatic	x (x.x)	x (x.x)	x (x.x)
Allergies	x (x.x)	x (x.x)	x (x.x)
Psychological/Psychiatric	x (x.x)	x (x.x)	x (x.x)
Other	x (x.x)	x (x.x)	x (x.x)

Percentages are based on the number of patients in each starting dose and overall.

If a medical history event of the same Body System Code is reported multiple times for a patient, it is counted only once.

Program: <program name (date, time)>, Path: <path>

Table B.14.1.5.1 Major Protocol Deviations (ITT Population)

Protocol Deviation Categories	Number of patients (%)		Overall (N = n)

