Table B.14.2.1.5.3 Proportion of patients Achieved CDA at or Prior to Week 5 without prednis(ol)one >0.5 mg/kg – Subgroup – Pemphigus History (PP Population)

Note: Subgroups are: ‘Newly diagnosed (\leq 6 months from screening)’, ‘Relapsed (>6 months from screening)’

Additional footnote: Newly diagnosed is defined as subjects who were diagnosed at most 6 months prior to date of screening, otherwise the subject is relapsed.

Table B.14.2.1.6.1 Proportion of patients Achieved CDA at or Prior to Week 5 without prednis(ol)one >0.5 mg/kg – Subgroup – Baseline Pemphigus Anti-DSG Profile (mITT Population)

Table B.14.2.1.6.2 Proportion of patients Achieved CDA at or Prior to Week 5 without prednis(ol)one >0.5 mg/kg – Subgroup – Baseline Pemphigus Anti-DSG Profile (Completer Population)

Table B.14.2.1.6.3 Proportion of patients Achieved CDA at or Prior to Week 5 without prednis(ol)one >0.5 mg/kg – Subgroup – Baseline Pemphigus Anti-DSG Profile (PP Population)

Note: Subgroups are: ‘Pemphigus Vulgaris (PV)’, ‘Pemphigus foliaceus (PF)’ and ‘Negative anti-DSG profile’

Table B.14.2.1.7.1 Proportion of patients Achieved CDA at or Prior to Week 5 without prednis(ol)one >0.5 mg/kg – Subgroup Analysis – Baseline Pemphigus Severity (mITT Population)

Table B.14.2.1.7.2 Proportion of patients Achieved CDA at or Prior to Week 5 without prednis(ol)one >0.5 mg/kg – Subgroup Analysis – Baseline Pemphigus Severity (Completer Population)

Table B.14.2.1.7.3 Proportion of patients Achieved CDA at or Prior to Week 5 without prednis(ol)one >0.5 mg/kg – Subgroup Analysis – Baseline Pemphigus Severity (PP Population)

Note: Subgroups are: ‘Mild at Baseline’, ‘Moderate at Baseline’

Additional footnote: Based on PDAI total activity score. For newly diagnosed patients: Mild is 0 to 14 and Moderate is 15 to 44. For relapsed patients: Mild is 0 to 8 and Moderate is 9 to 24.

Table B.14.2.2.1.1 Cumulative Incidence of Patients Achieved CDA by Visit – Cumulative Incidence (mITT Population)

Visit	Achieved CDA	400 mg QD (N = n)	400 mg BID (N = n)	600 mg BID (N = n)	Overall (N = n)
SCREENED	N achieved (%)	x (x.x)	x (x.x)	x (x.x)	x (x.x)
	- 80% CI	x.xx, x.xx	x.xx, x.xx	x.xx, x.xx	x.xx, x.xx
	- 95% CI	x.xx, x.xx	x.xx, x.xx	x.xx, x.xx	x.xx, x.xx
WEEK 1 DAY 1	Cumulative N achieved (%)	x (x.x)	x (x.x)	x (x.x)	x (x.x)
	- 80% CI	x.xx, x.xx	x.xx, x.xx	x.xx, x.xx	x.xx, x.xx
	- 95% CI	x.xx, x.xx	x.xx, x.xx	x.xx, x.xx	x.xx, x.xx
WEEK 1 DAY 2	Cumulative N achieved (%)	x (x.x)	x (x.x)	x (x.x)	x (x.x)

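### The shell footnote for the Part B severity subgroup contradicts the cut at PDAI 15 used elsewhere in the SAP and, followed as written, leaves some eligible scores in no row

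*SAP*

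**What the plan says.** **Cut-offs.** Section 5.4.1.1 of the Part B SAP defines the severity subset of the primary endpoint as "PDAI < 15 (mild-moderate) vs PDAI ≥ 15 (moderate-severe) at baseline". Section 5.1.3 and Table B.14.1.3.1 use the same cut and labels. Listing B.16.2.1.7 also cuts at 15, though it labels the two groups mild and moderate.

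The shells for the severity analysis itself, Tables B.14.2.1.7.1 to B.14.2.1.7.3, say something else. The row note reads "Note: Subgroups are: ‘Mild at Baseline’, ‘Moderate at Baseline". The footnote, which is based on the PDAI total activity score, gives "For newly diagnosed patients: Mild is 0 to 14 and Moderate is 15 to 44", followed by "For relapsed patients: Mild is 0 to 8 and Moderate is 9 to 24".

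**Visit.** For the same subset, Section 5.4.1.1 adds "If screening PDAI is not available use Week 1 Day 1 Pre-dose", which puts screening first. Section 3.4.1 states the general PDAI baseline: "The value measured at Week 1 Day 1 pre-dose will be used as the Baseline value", with screening as the fallback. The footnote for severity in Table B.14.1.3.1 agrees with 3.4.1: "Result at Week 1 Day 1. If Week 1 Day 1 is missing, then the Screening result is used".

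**Population.** Protocol inclusion criterion 1 admits "mild-moderate PV in Part A (PDAI 8 to 45) and mild-severe PV in Part B (PDAI 8 to 60"). Appendix 1B of the protocol defines severe PV as a PDAI of 45 or more.

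**The concern.** Section 5.4.1.1 presents the subset analyses as a check on the robustness of the primary result, and the protocol (Sections 11.5.3 and 11.9.1) names disease severity as an example subgroup. A programmer working from the shell would produce a different analysis from one working from the text.

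Both Moderate bands in the shell have an upper limit and no row follows them. The subgroup shells base percentages on the number in each subgroup, so a patient above the limit leaves numerator and denominator alike. The Moderate row would then describe response with the highest scores removed, and the two rows need not add up to the analysis population. Part B is also the part whose entry range was widened upward, from 45 to 60.

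The visit order is a second, smaller inconsistency. Screening can precede the first dose by up to 28 days. A patient whose screening and Day 1 scores lie on opposite sides of 15 would be in one stratum in the subset table and in the other in the disease history table.

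**Working it through.** The plan states no figure for this analysis. Its one design figure, an 80% CI of ±13% with 25 patients at a 50% response rate, reproduces as 1.2816 × √(0.5 × 0.5 / 25) = 0.128, but it plays no part here.

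**Inputs**
- Eligible range in Part B: PDAI 8 to 60 (protocol inclusion criterion 1), which is 60 − 8 + 1 = 53 integer scores.
- Text rule: below 15, or 15 and above (Part B SAP 5.4.1.1).
- Shell rule: 0–14 and 15–44 if newly diagnosed; 0–8 and 9–24 if relapsed (Tables B.14.2.1.7.x).
- Severe: 45 or more (protocol Appendix 1B).

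**Each eligible score sorted under both rules**

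| History | Scores | Text rule | Shell rule | Number of scores |
|---|---|---|---|---|
| Newly diagnosed | 8–14 | lower | Mild | 7 |
| Newly diagnosed | 15–44 | upper | Moderate | 30 |
| Newly diagnosed | 45–60 | upper | no row | 16 |
| Relapsed | 8 | lower | Mild | 1 |
| Relapsed | 9–14 | lower | Moderate | 6 |
| Relapsed | 15–24 | upper | Moderate | 10 |
| Relapsed | 25–44 | upper | no row | 20 |
| Relapsed | 45–60 | upper | no row | 16 |

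Check: newly diagnosed 7 + 30 + 16 = 53; relapsed 1 + 6 + 10 + 20 + 16 = 53.

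**Results**
- The text rule leaves no score unclassified.
- The shell leaves 16 scores without a row for newly diagnosed patients and 20 + 16 = 36 for relapsed patients. Every score in the protocol's severe range is among them, whatever the history.
- Six relapsed scores (9–14) change group. Relapsed Mild keeps a single eligible value, 8.

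**Does the gap depend on the upper limit of 60?** Section 2.2 of the Part B SAP restates the range as 8 to 45 for each part, which disagrees with the protocol. Under that narrower range (38 scores), relapsed scores of 25–45 (21 values) and a newly diagnosed score of 45 (1 value) still have no row.

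**Visit rule.** Sections 3.4.1 and 5.4.1.1 use the same two visits in opposite order, so they differ only for a patient with both scores present and on different sides of a cut. The Part A SAP (Section 8.2.11) and the Part A severity subgroup shell also take screening first, so the Part B sentence looks carried over.

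**The case against.** The case for leaving this alone has real content.

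- **It is one footnote.** Two text sections, the disease history table and a listing all cut at 15, and Section 6 allows the shells to be adjusted. It is true that the conflict is isolated. But that permission concerns layout and fitting the data collected. A footnote that defines strata is an analysis rule, and it sits on the very tables at issue.
- **Severe patients are not lost to the trial.** A reader might infer that response in severe disease could no longer be described. The documents do not support that. These patients stay in the overall primary estimate and in the per-patient panel plots of PDAI, dose and steroid (Section 5.4.1). They also stay in Listings B.16.2.1.7, B.16.2.6.1, B.16.2.6.5 and B.16.2.6.10, which give baseline PDAI, response status and PDAI by visit. The protocol allows further severity subgroups.
- **Mismatch with the disease history table proves little.** Table B.14.1.3.1 uses the ITT population by starting dose. The subset tables use the mITT, Completer and PP populations by dose level. Totals can differ by design even with identical cut-offs.
- **Screening first is defensible.** A reader might call it an error, but it matches the Part A subgroup, and the protocol allows Parts A and B to be combined where appropriate. What stands is that the Part B SAP gives two visit rules and does not say that the difference is intended.
- **Stakes are low.** This is a descriptive subset in a pilot of about 25 patients per part, with no hypothesis testing and no decision rule. That stands, and it sets the grade.

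**Conclusion.** The footnote to Tables B.14.2.1.7.1 to B.14.2.1.7.3 is wrong as written, and the consequence is minor. It contradicts Sections 5.4.1.1 and 5.1.3, Table B.14.1.3.1 and Listing B.16.2.1.7. Followed literally, it drops scores of 45 to 60 for everyone and 25 to 44 for relapsed patients, and it moves relapsed scores of 9 to 14 upward.

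The sizes above count score values. It would be tempting to read 36 of 53 as a share of patients, but the documents give neither a baseline PDAI distribution nor the split between newly diagnosed and relapsed, so the number of patients affected is unknown and could be zero. The sorting also assumes that the eligibility PDAI is the total activity score named in the footnote, and that the score used for the subgroup lies within the entry range. A Day 1 score may not.

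The order of visits is an inconsistency to reconcile. The documents do not show that either choice is mistaken.

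**What to change.** 1. In Tables B.14.2.1.7.1 to B.14.2.1.7.3, replace the history-dependent footnote and the two row labels with the 5.4.1.1 rule: below 15 (mild-moderate) and 15 or more (moderate-severe). Give Listing B.16.2.1.7 the same labels. Severity then no longer depends on the newly diagnosed definition, which the SAP gives as 180 days in Section 5.1.3 and as 6 months in 5.4.1.1.
2. State one visit rule for severity and use it in 5.4.1.1, the shells and the listing. The SAP's own baseline in 3.4.1 (Day 1 pre-dose, else screening) is the natural default. Add a note that the Part A subgroup took screening first, for anyone comparing or pooling the parts.
3. Step 1 gives every patient a row but pools severe with moderate disease. If response in severe disease is to be shown separately, split the upper row into 15–44 and 45 or more, using the protocol's own severe threshold for all patients, and report the counts, which may be small.
4. In the same edit, reconcile the 8 to 45 range in Section 2.2 with the protocol's 8 to 60 for Part B.

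The cost is a few lines of SAP text and one programming note. No new data are needed, and the overall primary estimate does not change.
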